**Secondary Aims:**

1. To assess pain scores by VAS in primary C-section patients using the adherent soft silicone silver impregnated anti-microbial occlusive foam dressing silver-impregnated dressing

2. To assess cosmetic appearance of the incision based on Stony Brook scar evaluation scale scores for those patients using the adherent soft silicone silver impregnated anti-microbial occlusive foam dressing silver-impregnated dressing.

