## **Methods and Materials**

### *Study Population and Recruitment*

This single-center, prospective, observational trial will include women between 18 and 45 years of age with viable pregnancies (24 weeks or greater) undergoing primary cesarean delivery at Loyola University Medical Center, Maywood, Illinois.

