Obstetric physicians will perform a standardized physical examination of the wound dressing on each postoperative day, at 7 days post-operatively on dressing removal, and the wound will be examined also at the standard 6 weeks postpartum examination for patients in both groups. For patients who do not return for their postpartum visit at 7 days and 6 weeks, a standardized phone evaluation will be conducted by trained study personnel; any report of wound complication will be documented in the medical record.

The **primary outcome variable** will be a composite of wound disruption and/or infection occurring within 4 weeks postoperative (**wound complication rate: SSI**). Wound disruption will be defined as any separation of the wound (ranging from small skin defects to entire separation of the wound) and subcutaneous skin dehiscence, i.e. from seroma or hematoma. Wound infection will be classified by the Centers for Disease Control and Prevention (CDC) guidelines (22). **Secondary outcomes will include:** pain measured at 24h, 48 h, 7 days at dressing removal, and 6 weeks after cesarean delivery using a ten-point visual analog scale (VAS) from 0 to 10 (with 0 indicating no pain and 10 indicating worst conceivable pain), cosmesis score (as defined by the Stony Brook Scar Evaluation Scale (23)) 7 days and 6 weeks postoperatively, mobility assessment, readmission to the hospital, post discharge fever or antibiotic therapy, and additional clinic visits (both routine and unscheduled). Please see Figures 1 and 2. Additionally, all patients will be queried on degree of satisfaction on a scale of 1-10 as will clinicians queried on ease of use.

In addition, deidentified demographic and outcome data on those who had a primary csection with transverse incision closed in a subcuticular fashion who did not participate in the silver dressing during the same time period were collected.

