## Analysis Plan

### Statistical Considerations:

*Data Management:* Data forms collected will be converted to equivalent electronic data entry forms with use of REDCap. REDCap (Research Electronic Data Capture) is a secure, web-based application designed to support data capture for research studies, providing: 1) an intuitive interface for validated data entry; 2) audit trails for tracking data manipulation and export procedures; 3) automated export procedures for seamless data downloads to common statistical packages; and 4) procedures for importing data from external sources. REDCap is hosted on secure servers located in the Loyola Medical School Campus and supported by the IT department. Project staff will be trained in the use of REDCap for entry of study data. Appropriate logic and limits checking (including cross-form validity checks) will be implemented in REDCap to facilitate accurate and consistent data entry. Study information within the virtual environment will be available for participant tracking activities such as production of result and reminder letters, scheduling of interim telephone contacts, and scheduling and tracking of follow-up visits.

*Statistical Analysis:* It has been argued that the current rate of wound complication is about 10%. We postulate that patients following this treatment will experience a lower rate of wound complication. The incidence of infection will be estimated as the proportion of patients who developed infection by the end of the study period. Confounded-adjusted rates will be estimated using generalized linear models (identity link, binomial family). We will apply a one-sample, two-sided, 5% significance Z-test to compare the rate of infection with the new treatment to the historical 10%.

In addition, comparisons between the silver dressing group and the contemporary comparison group will be made by T-test, Chi-square, Fishers exact test, logistic regression modeling.

[figure not shown]
*Sample Size/Power Justification:* As stated above, we are interested in demonstrating that the rate of wound complication is lower than the historical 10% value found in the literature. We will accrue **185 patients** to detect a 5% difference (10% vs 5%) using the one-sample Z-test with 80% statistical power. Testing via the generalized linear model to adjust for confounders will increase the statistical power to detect differences.

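### The plan lists no confounder-adjusted method for continuous outcomes, so any pain, scar or satisfaction score compared between the dressing group and the non-participants would be compared unadjusted

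*Combined protocol and SAP*

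**What the plan says.** - **Design.** Study Population and Recruitment: "This single-center, prospective, observational trial will include women between 18 and 45 years of age". There is no randomisation. Under Methodology of Measurements, consenting eligible women receive the silver dressing and women not participating receive a standard one.
- **Comparison group.** The end of Methodology of Measurements describes "deidentified demographic and outcome data on those who had a primary csection with transverse incision closed in a subcuticular fashion" among women "who did not participate in the silver dressing during the same time period were collected". Its size is not given, nor is it said which outcomes were obtained.
- **Between-group methods.** Statistical Analysis gives one pooled list: "comparisons between the silver dressing group and the contemporary comparison group will be made by T-test, Chi-square, Fishers exact test, logistic regression modeling". No method is tied to an outcome and no covariates are named.
- **Adjustment.** The same section states "Confounded-adjusted rates will be estimated using generalized linear models (identity link, binomial family"), which concerns a binary outcome.
- **Continuous outcomes.** Methodology of Measurements lists "pain measured at 24h, 48 h, 7 days at dressing removal, and 6 weeks after cesarean delivery", "cosmesis score (as defined by the Stony Brook Scar Evaluation Scale (23)) 7 days and 6 weeks postoperatively", and satisfaction on a 1-10 scale.
- **Secondary Aims.** The pain aim reads "To assess pain scores by VAS in primary C-section patients using the adherent soft silicone silver impregnated anti-microbial occlusive foam dressing". The scar aim is likewise worded for dressing users only. Neither names a comparator.

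**The concern.** Women enter one group or the other by agreeing or not agreeing to take part, so the groups may differ in ways that affect pain, healing and satisfaction. The documents give two reasons to take this seriously. The exclusion criteria remove women with intrapartum fever from the participants, but the description of the comparison group does not repeat that exclusion; as written, febrile women can appear only among the non-participants. The background also cites a higher burden of comorbidity in the silver-dressing group as a limitation of an earlier retrospective study.

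The plan provides adjustment for rates but nothing equivalent for scores. If a score is compared between the groups with the listed tools, the estimated difference mixes any dressing effect with case mix.

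**Working it through.** **Step 1: which listed method can serve a continuous score?**

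| Method in the plan | Outcome type | Can adjust? |
|---|---|---|
| T-test | continuous | no |
| Chi-square, Fisher's exact | categorical | no |
| Logistic regression | binary | yes, but no covariates named |
| Binomial GLM, identity link | binary (rates) | yes, but no covariates named |

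The continuous row holds one method, and it is unadjusted.

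**Step 2: is there a figure in the plan to reproduce?** No. The plan gives no SD, expected difference or power for any score, and no comparison-group size. The 185 patients are the accrual target for the one-sample primary test; here 185 serves only as the size of the dressing group.

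**Step 3: illustration of the bias.** Assumed, not from the documents: VAS SD 2.5; no dressing effect; one unadjusted binary factor; comparison group of 185 or 370.

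- Bias = imbalance in prevalence × effect of the factor on VAS.
- SE = 2.5 × √(1/185 + 1/n₂), which is 0.260 for n₂ = 185 and 0.225 for n₂ = 370.
- False-positive rate = P(|Z + bias/SE| > 1.96).

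| Imbalance | Effect (VAS points) | Bias | n₂ = 185 | n₂ = 370 |
|---|---|---|---|---|
| 10 percentage points | 0.5 | 0.05 | 5.4% | 5.6% |
| 20 percentage points | 1.0 | 0.20 | 12.0% | 14.4% |
| 30 percentage points | 1.5 | 0.45 | 41% | 52% |

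For the last cell, 0.45/0.225 = 2.00, so the rate is about P(Z > −0.04) = 52%. A larger comparison group makes the error rate worse, because the SE shrinks and the bias does not.

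**Step 4: the same without choosing an SD.** With 185 per group and the bias expressed in SD units, the rate is 8% at 0.05 SD, 16% at 0.10 SD and 49% at 0.20 SD. The three biases in the table equal 0.02, 0.08 and 0.18 SD (0.05, 0.20 and 0.45 divided by 2.5). A smaller SD would raise the rates and a larger one would lower them.

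**The case against.** A reader might infer that the plan compares pain and scar scores by T-test, that both secondary aims depend on that comparison, and that differences will be credited to the dressing. The documents do not support this.

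- No test is tied to any score. The comparison data include demographics, so the T-test may be meant for baseline variables such as age.
- Both secondary aims concern dressing users only. A mean with an interval in that group answers them without any between-group test.
- It is not stated that non-participants completed a VAS or a scar scale. The 7-day pain score is tied to dressing removal, yet the standard dressing comes off by 24 hours, so that time point fits only the study dressing. The wound is examined at 6 weeks in both groups, which leaves a comparison possible but not established.
- The plan calls itself observational and nowhere says that secondary differences will be read causally.
- Every input to the illustration other than the 185 is assumed.

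All of this stands, and it makes the point conditional. It does not remove the gap. The plan sets no baseline-only limit on the T-test, and it says that outcome data were collected on non-participants. If the T-test is for baseline only, there is no between-group method for scores at all. Either way the same paragraph needs the same edit.

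The plan also does not specify separate tests at each visit, so ignoring repeated measurements is not an error it has committed; a mixed model is simply the better choice if VAS is compared.

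**Conclusion.** The concern holds in conditional form. The groups are self-selected, and the plan offers no adjusted analysis for a continuous outcome. If such an outcome is compared between them as written, case-mix differences remain in the estimate. Neither the size nor the direction of the bias can be derived from the documents. The range of about 5% to 52% rests on an assumed SD of 2.5, no dressing effect, imbalances of 10 to 30 percentage points, covariate effects of 0.5 to 1.5 VAS points and a comparison group of 185 or 370; it shows sensitivity and is not a forecast. The primary test against the historical 10% is not affected. The outcomes concerned are secondary, but a better method is available at little cost, so the change is worth making.

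**What to change.** In the Statistical Analysis paragraph:

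1. Limit the T-test to describing baseline variables.
2. State which continuous outcomes are available in both groups. For those, use linear regression, with ordinal regression for the 0-5 scar score and, for VAS, one mixed model over the visits with group, time and group-by-time.
3. Name the baseline covariates, restricted to those held for both groups: for example age, BMI, comorbidities, labor or ruptured membranes, and intrapartum fever. Alternatively, apply the fever exclusion to the comparison group. Use the same covariates in the logistic model, which at present names none.
4. For any instrument that non-participants did not complete, report the dressing-group mean with a 95% interval and make no group comparison. This answers the secondary aims as worded.

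First confirm what the de-identified comparison data contain. The baseline evaluation is specified for study participants; for non-participants the plan mentions only demographic and outcome data. A covariate missing for them cannot be adjusted for, and that limitation should be reported.

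The cost is revised wording and a little more analysis work. The downside is that results will depend on the chosen covariates, which is why they should be named in the plan.

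### The 185 patients match a one-sided 5% test; under the two-sided 5% Z-test the plan specifies, power for 10% vs 5% is about 66–68%, not 80%

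*Combined protocol and SAP*

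**What the plan says.** Both statements are in the combined protocol and SAP, Analysis Plan, under Statistical Considerations.

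- The Statistical Analysis paragraph sets the test: "We will apply a one-sample, two-sided, 5% significance Z-test", with the historical 10% as the reference value.
- The Sample Size/Power Justification paragraph gives the aim as showing that "the rate of wound complication is lower than the historical 10% value found in the literature". It then sets the size, "We will accrue 185 patients", and says this is enough "to detect a 5% difference (10% vs 5%) using the one-sample Z-test with 80% statistical power".

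The sample-size paragraph does not repeat the significance level or the number of sides, so both must come from the Statistical Analysis paragraph. It makes no allowance for unevaluable patients. It adds that adjusting for confounders in a generalized linear model will raise power, but gives no amount.

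**The concern.** Everything needed to check the power claim is in the plan: null rate, alternative rate, level, sides, sample size and power. Together they should reproduce one another, and they do not. The size agrees with a one-sided 5% calculation, while the analysis is expressly two-sided.

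This is the plan's only power statement, and it concerns the main hypothesis test. If the true rate is 5%, a reader told the design has 80% power expects it to be missed one time in five. The design as specified would miss it about one time in three. A non-significant result could then be taken as stronger evidence against the dressing than the study can supply.

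**Working it through.** **Inputs, all from Statistical Considerations:** p0 = 0.10, p1 = 0.05, difference 0.05, two-sided level 5% (z = 1.960), power 80% (z = 0.8416), n = 185. The standard deviations per patient are √(0.10 × 0.90) = 0.3000 under the null and √(0.05 × 0.95) = 0.2179 under the alternative.

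**Formulas** (one-sample proportion Z-test, standard error under the null):

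- n = [(z_α √(p0 q0) + z_β √(p1 q1)) / (p0 − p1)]²
- power = Φ[((p0 − p1)√n − z_α √(p0 q0)) / √(p1 q1)]

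**Step 1. Reproducing the plan's figure.** It comes out only with the one-sided critical value 1.645:

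- n = [(1.645 × 0.3000 + 0.8416 × 0.2179) / 0.05]² = (0.6769 / 0.05)² = 183.3, so 184.
- Power at 185 = Φ[(0.6801 − 0.4935) / 0.2179] = Φ(0.856) = 80.4%.

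**Step 2. The test as specified, two-sided 5%:**

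- n = [(1.960 × 0.3000 + 0.8416 × 0.2179) / 0.05]² = (0.7714 / 0.05)² = 238.03, so 239. The shortfall is 239 − 185 = 54.
- Power at 185 = Φ[(0.6801 − 0.5880) / 0.2179] = Φ(0.4225) = 66.4%.

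**Step 3. Exact check at n = 185.** The two-sided test rejects downwards at 10 or fewer events (Z = −2.08); 11 events gives Z = −1.84 and does not reject.

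- P(X ≤ 10 | 185, 0.05) = 67.8%, the exact power.
- P(X ≤ 10 | 185, 0.10) = 1.9%, the lower-tail error.

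**Step 4. What 185 can detect.** Solving the two-sided power equation for 80% at n = 185 gives a true rate of 0.0441 by normal approximation and 0.0443 by exact calculation, that is, about 4.4%.

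**Step 5. Could another two-sided formula give 185?** None of those tried does:

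| Two-sided 5% variant | n for 80% power |
|---|---|
| Variance at p1 only (Wald planning form) | 150 |
| Arcsine | 212 |
| Mean of the two variances | 216 |
| Variance at 0.075 | 218 |
| Null variance for α, alternative variance for β | 239 |
| The same with continuity correction | 258 |
| Null variance only | 283 |

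**The case against.** The strongest reply is that the plan never says which standard error its Z-test uses. It also plans identity-link binomial models, whose usual Wald test takes the variance from the observed rate. A two-sided Wald test at n = 185 rejects at 11 or fewer events (Z = −2.33 at 11, −1.94 at 12). Its exact power is 78.3%, within two points of the claim, and its total exact error is 4.65%, inside the stated 5%. That is a fair point, and it means the 66–68% figure depends on the null-variance form of the test.

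It does not rescue the claim:

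- The power is still below 80%.
- The gain comes from a lower-tail error of 3.6%, against the nominal 2.5%. The lower rejection region is the same as that of the one-sided 5% null-variance test.
- The error rate is unstable: one more patient (n = 186) moves the limit to 12 events and total error to 7.3%.
- The Wald planning formula gives 150 patients, and 87.7% power at 185, so it does not explain the plan's number.

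Three smaller points can be granted. A one-sided origin for 185 is an inference, since the formula gives 184 and the documents do not show the calculation. The figure 239 is a normal-approximation result; exact power at 239 is 78.1%. And the primary aim is worded as estimating a rate, in an observational study, so the error changes no procedure or endpoint. The plan nevertheless specifies a test and claims a power for it.

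The remark on model adjustment carries no figure and played no part in deriving 185, so it cannot make up 12 to 14 points of power.

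**Conclusion.** The concern holds. With the two-sided 5% one-sample Z-test in its standard null-variance form, 185 patients give 66.4% (approximate) or 67.8% (exact) power for 10% vs 5%. The type II error is 32–34%, not 20%. The stated 80% agrees with a one-sided 5% test.

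This rests on the plan's own rates, level and sample size, on the null-variance standard error, and on all 185 patients being evaluable. With the observed variance, exact power is 78.3%, with the error-rate problems described above. Any loss of evaluable patients would generally lower power further. The power statement needs correcting before it is relied on.

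**What to change.** Keep the two-sided 5% test and the 185 patients, and replace the power sentence with wording such as: *Using a two-sided 5% one-sample Z-test with the standard error under the 10% null, 185 evaluable patients give about 66–68% power to detect 10% vs 5%, and 80% power to detect 10% vs about 4.4%.* Naming the standard error matters, because the restated power is correct only for that form of the test.

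If a one-sided 5% test was what the study team intended, say so in the Statistical Analysis paragraph instead, so that test and size agree. Power at 185 is then 80.4% by normal approximation and 78.3% exactly.

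The remark that model adjustment will increase power should not be used to support the 80% figure unless a gain is quantified.

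The cost is one corrected sentence and a less favourable stated power. No patients, procedures or endpoints change. Restoring 80% power with the two-sided test would instead take about 54 more patients, but the correction does not require it.

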### ***Exclusion criteria:***

- Patients with an allergy to silver
- Inability to obtain informed consent
- Staples
- Repeat C-section
- Vertical skin incision
- Intrapartum fever of 100F or >

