### **Methodology of Measurements:**

Women who are admitted to labor and delivery or the antepartum unit will be invited to participate. Those who require a cesarean delivery will undergo standard perioperative management: surgical skin preparation with Chloroprep solution, vaginal betadine prep, and prophylactic antibiotics. Women, who consented to participate, have a Pfannensteil incision and subcuticular skin closure will have the study dressing, *Mepilex Border AG*, placed.

*Mepilex Border Ag* is produced by Molynycke Health Care, and is a commercially available adherent soft silicone anti-microbial occlusive foam silver-impregnated dressing. This dressing was designed to aid in healing of wounds at high risk for infection, such as postoperative wounds, with provision of localized antimicrobial

activity. The high risk for wound infection and complications in our population led to selection of this dressing. No contraindications have been identified.

The cesarean delivery technique may differ among health care providers at our institution but generally follows usual practice, including perioperative prophylactic antibiotics and surgical skin preparation with Chloroprep solution, vaginal betadine prep, saline irrigation of the subcutaneous layer, and the use of cautery to obtain hemostasis. In addition, the subcutaneous layer is reapproximated with 3-0 Vicryl for all women with a subcutaneous layer greater than 2.0 cm. The skin will be closed with continuous absorbable suture, e.g. 3-0 Vicryl or Monocryl. Women with subcuticular suture will have adhesive strips applied with benzoin prior to the placement of the dressing.

If not participating, the wound will be dressed with a standard dressing. The standard dressing will be removed by 24 hours postoperatively. The study dressing will be removed during the first 7 days post-op only to allow/require dressing changes due to clinical signs of infection, leakage, or if the dressing falls off. Otherwise the study dressing will be removed on postoperative day 7 by a physician.

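### The claimed power gain from GLM adjustment is unsupported: the powered test sets one all-treated cohort against a fixed 10%, with no covariates or reference case mix named

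*Combined protocol and SAP*

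**What the plan says.** All the main statements are in the Analysis Plan, Statistical Considerations.

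- **Deciding test.** "We will apply a one-sample, two-sided, 5% significance Z-test", comparing the dressing cohort with 10%. The aim is a rate "lower than the historical 10% value found in the literature".
- **Sample size.** 185 patients, for 10% against 5% with 80% power by that one-sample test.
- **Adjusted rates.** "Confounded-adjusted rates will be estimated using generalized linear models (identity link, binomial family"). No covariates, reference values or target population are given.
- **Power claim.** The sample-size paragraph ends: "Testing via the generalized linear model to adjust for confounders will increase the statistical power to detect differences". No figure or calculation accompanies it.
- **Separate comparison.** As an additional analysis, "comparisons between the silver dressing group and the contemporary comparison group will be made by T-test, Chi-square, Fishers exact test, logistic regression modeling". No sample size or power is given for it.

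Background and Significance lists risk factors for wound complications, but nothing links that list to the model.

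**The concern.** Covariate adjustment can sharpen a comparison between groups by improving the precision of a treatment coefficient. It can also reduce confounding when the covariate distribution is known on both sides. The one-sample test has neither feature: every patient has the dressing, and the comparator is a constant with no case mix attached.

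Two misreadings are at stake. A reader may believe that the trial has power in reserve beyond the Z-test. A reader may also take the adjusted rate as corrected for differences between this cohort and the patients behind the 10%. Those differences could run in either direction. The Methodology of Measurements section says "The high risk for wound infection and complications in our population led to selection of this dressing", which points to a higher baseline risk, while the exclusion of "Intrapartum fever of 100F or >" points to a lower one.

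The sentence also leaves open a second, unspecified test of the primary question.

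**Working it through.** **Inputs from the plan.** n = 185, null rate 0.10, alternative 0.05, two-sided 5%. Prevalences and effects of risk factors are not in the documents; those used below are assumptions.

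**1. The plan's own figure.** n = [z_α√(0.10×0.90) + 0.8416√(0.05×0.95)]² / 0.05². With z_α = 1.960 this gives 238.03, so 239; with z_α = 1.645 it gives 183.3, so 184. The stated 185 matches a one-sided 5% calculation. That mismatch is a separate issue. For the stated two-sided test at n = 185, with the SE at 10%:

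Power = Φ[(0.05√185 − 1.96×0.30)/√0.0475] = Φ(0.0921/0.2179) = Φ(0.4225) = 66.4% (exact binomial 67.8%).

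**2. Rate averaged over the cohort, planned model.** The identity-link binomial GLM was simulated at n = 185 with assumed obesity (40% prevalence, +3 points) and diabetes (12%, +5 points).

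- Among usable fits, adjusted and crude rates differed by up to about 0.35 points (0.38 the largest in repeat runs).
- Their sampling SDs were equal: about 1.55 points at a true 5% and 2.2 points at a true 10%.
- Some fits failed to converge or gave risks outside 0 to 1: about 16% to 26% at a true 5% and 5% to 10% at a true 10%, depending on the fitting procedure.

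The estimator is thus essentially the crude proportion with the same variance.

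**3. Covariates treated as fixed.** The assumed effects give an individual-risk variance of 0.4×0.6×0.03² + 0.12×0.88×0.05² = 0.00048 (SD 2.2 points), or 0.00048/0.0475 = 1.0% of the outcome variance. The nominal power gain is 0.1 to 0.6 points; at an assumed SD of 5 points it is 0.4 to 3.1. Reaching 80% at n = 185 would require removing 1 − 185/238 = 22% of the variance.

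Nor is this gain free. With one assumed binary risk factor (40% prevalence, risk ratios 1 to 4) in a saturated model, where the link does not matter, the Wald test with covariates fixed moved as follows:

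| True rate | Crude Wald rejection | Covariates fixed |
|---|---|---|
| 5% | 0.78–0.80 | 0.78–0.84 |
| 10% | about 0.05 | up to 0.07 |

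A larger simulation with a logistic model (not the planned link) showed the same pattern. Rejection at 5% rose from 78.3% to 82.4%, and wrong claims of benefit at a true 10% rose from 3.7% to 4.6%, against a nominal 2.5%. Covariates with no effect at all still raised these from 78.1% to 79.4% and from 3.7% to 4.1%.

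**4. Standardising to another case mix.** Take a risk ratio of 3, prevalence 40% and cohort rate 5%. The stratum risks are 0.05/(0.6 + 0.4×3) = 2.78% and 8.33%.

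- Reference prevalence 60%: the rate tested is 0.4×2.78 + 0.6×8.33 = 6.1%; rejection 51%.
- Reference prevalence 20%: the rate tested is 0.8×2.78 + 0.2×8.33 = 3.9%; rejection 95%. With this mix, rejection is 28% when the cohort's true rate is 10%.

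Crude rejection in the same setting is 79%. The reference mix decides the direction, and the plan states none.

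**5. A related but separate point.** The plan does not say which SE the Z-test uses. At 11/185 = 5.95%, the SE at 10% gives z = −1.84 and p = 0.066; a Wald SE gives z = −2.33 and p = 0.020. This would be true without the GLM sentence.

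**The case against.** **The study has a comparator.** It does: the contemporary non-participants. Logistic regression is itself a GLM, so the power sentence may simply be misplaced. But it closes the one-sample paragraph, and the contemporary comparison is introduced as an addition with its own methods and no sample size. A reader should not infer that the study lacks any treatment contrast; only the powered test does.

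**Adjustment can reduce the variance.** Inference conditional on the cohort's own covariates is a recognised choice, and under it the smaller SE is legitimate. This stands in part. It concerns a different target from the cohort-average rate as a sampled quantity, the plan does not choose it, and the nominal gain is small under the assumptions tried.

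**A flat denial is too strong.** A reader might conclude that adjustment can never change power here. The documents do not support that: with no target stated, the effect is undetermined. The absence of a gain is shown only for the rate averaged over the cohort.

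**The sentence is inconsequential.** The 185 does not rest on it, and the Z-test sizes the trial. That is right, and it limits the weight of the point. It would be wrong to infer that the sample size fails because of this sentence.

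**Conclusion.** The plan asserts a property of its primary test that the design does not support. For the rate averaged over the cohort, the planned model gives essentially the crude estimate and the same sampling variance. For any other target, power could rise or fall with a reference mix that is not specified. Standardising to an external case mix could in principle reduce measured confounding, but the documents supply no covariate data behind the 10%, so the adjusted rate cannot be described as corrected for historical differences.

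The conclusion that the gain is unsupported rests on the text alone. The sizes (differences up to about 0.35 points, nominal gains of 0.1 to 3.1 points) rest on assumed prevalences and effects. The claim certainly cannot be relied on to cover the distance between 66.4% and 80%; that shortfall and the unstated SE are separate matters and are not counted here. The correction is worth making but moderate in weight.

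**What to change.** 1. Delete the power sentence.
2. State that the deciding test is the unadjusted one-sample test against 10% with the SE at 10%, or an exact binomial test, with a matching 95% interval (score or exact), and that no GLM-based test decides the primary result. The two agree at the boundary. Ten events give p = 0.037 and an upper limit of 9.7%. Eleven give p = 0.066 and an upper limit of 10.3% (score) or 10.4% (exact). If the exact test is chosen, state its convention: the equal-tailed exact interval pairs with a doubled-tail p (0.073 at 11 events).
3. Label any adjusted rate for the dressing group alone as descriptive, and state its covariates, its target population and what happens if the identity-link fit fails.
4. Use covariate adjustment in the planned logistic regression against the contemporary group, with a few covariates named in advance and recorded in both groups. For non-participants the protocol describes only "deidentified demographic and outcome data on those who had a primary csection with transverse incision closed in a subcuticular fashion"; BMI is listed among the examination items for participants and may not be available for the others. At a 5% rate the dressing group has about 185×0.05 = 9 events, so the model must be small.

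**Cost.** Items 1 to 3 are wording. Item 4 needs a check of which covariates exist in both groups. The sample size does not change; the plan gives up a claimed power gain that it cannot support.
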